#### **Secondary endpoints:**

During inpatient treatment: isolated calf muscle DVT; proximal DVT; symptomatic PE; fatal PE; total VTE events; postoperative mortality; leg skin injury; combination of major and clinically, relevant non-major bleeding; and compliance with IPC.

At 30 days after surgery:

- Combination of symptomatic, asymptomatic venous thrombosis of the lower, limbs and symptomatic PE;
- VTE-related mortality;
- Non-VTE-related mortality.

At 180 days after surgery:

- Combination of symptomatic, asymptomatic venous thrombosis of the lower limbs, and symptomatic PE;
- VTE-related mortality;
- Non-VTE-related mortality.

Following DUS, distal DVT is defined as incompressibility of the affected calf vein, re-occlusion of the previously affected calf vein in case of personal DVT history. Proximal DVT is defined as incompressibility of the affected popliteal and thigh veins, re-occlusion of previously affected popliteal and thigh veins in case of personal DVT history, no blood flow with color flow imaging. Superficial vein thrombosis is defined as incompressibility of the affected superficial vein (GSV and its branches and SSV and its branches). Isolated calf muscle DVT is defined as occlusion of any calf veins except PTV, ATV, and PeV (sural veins, soleal veins). Proximal DVT is defined as occlusion of popliteal and all further cranial venous segments up to the iliac veins (PV, FV, CFV, external iliac vein, common iliac vein). Pulmonary embolism will be suspected according to the classical clinical symptoms and verified with SPECT/CT or CTPA by specific defects of contrast.

Major bleeding is defined by the ISTH criteria as: fatal bleeding; bleeding that is symptomatic and occurs in a critical area or organ; extra-surgical site bleeding causing a fall in hemoglobin level of  $\geq 20$  g/L, or leading to transfusion of  $\geq 2$  units of whole blood or RDC, with temporal association within 24–48 h to the bleeding; surgical site bleeding that requires a second intervention; or surgical site bleeding that is unexpected and prolonged or sufficiently large to cause hemodynamic instability, as assessed by the surgeon.

Clinically relevant non-major (CRNM) is defined as any other bleeding, that does not match the criteria of major but needs some specific measures for hemostasis and/or interruption or preliminary abortion of anticoagulation.

Leg skin injury is defined as the appearance of skin hyperemia, blisters (and further erosions), and necrosis (and further ulceration) in the zone of contact with GCS, especially at the anterior surface of the ankle joint.

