### **Secondary objectives:**

- To study the effect of IPC on the asymptomatic venous thrombosis occurrence during inpatient treatment in prespecified groups of patients:
  - Surgical profile,
  - Type of surgery,
  - The urgency of surgery,
  - The radicalism of surgery,
  - Type of anesthesia,
  - Malignant or benign disorder;
  - Preoperative, postoperative or delayed start of LMWH injections,
  - Pre-operative or post-operative IPC application,
- To study the effect of IPC on the isolated calf muscle DVT occurrence during inpatient treatment;
- To study the effect of IPC on the proximal DVT occurrence during inpatient treatment;
- To study the effect of IPC on the symptomatic PE occurrence during inpatient treatment;
- To study the effect of IPC on the fatal PE occurrence during inpatient treatment,

- To study the effect of IPC on the total VTE events that occur during inpatient treatment,
- To study the effect of IPC on the leg skin injury occurrence during inpatient treatment;
- To study the effect of IPC on the major and clinically relevant non-major bleeding occurrence during inpatient treatment;
- To study the compliance with IPC applied in the suggested regimen-required night free-of-compression interval;
- To study the effect of IPC on the symptomatic and asymptomatic venous thrombosis of lower limbs, symptomatic pulmonary embolism occurrence, and VTE related and VTE-non-related mortality during outpatient treatment and rehabilitation 30 and 180 days after surgery.

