### 3. Design

A two-center, prospective, randomized (with independent allocation), open-label clinical trial with a blinded assessor for efficacy outcomes, enrolling patients at extremely high risk for postoperative VTE (Caprini score of 11 and more). The patients should be randomly allocated into two groups (experimental [IPC] group and control group) according to the VTE prophylaxis they received. Both groups will receive anti-embolic stockings and injections of LMWH, and patients in the IPC group additionally will receive IPC. The total duration of prophylaxis should amount of 1 month, and patients will be followed-up for 6 months with regular clinical examination and duplex ultrasound scans. Figure 1 represents the global design of the study.

[figure not shown]

**Figure 1.** The global design of the study.

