##### **4.1. Anti-embolic stockings**

Above-knee anti-embolic compression stockings fitted by the leg size should be applied before the surgery. In the case of elective surgery, the size should be fitted before,

and patients should be admitted to the hospital with their own stockings. In the case of emergent surgery, leg sizes should be obtained after admission, and the stockings should be received from the stocking bank. ECS should be applied round-the-clock during the inpatient period of treatment. After discharge, patients will be recommended to use stocking at night and during the long bed rest for 1 month. The manufacturer for the ECSs is not prespecified, so it is possible to use any available product. Stocking application should be controlled within standard medical care.

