#### **4.3. Sequential pneumatic compression**

Intermitted pneumatic compression should be applied with Cardinal Health™ Kendall SCD™ 700 Series Controller and Kendall SCD™ thigh-length Comfort Sleeves. The pumps will be provided by the Sponsor (10 pumps by Cardinal Health™), and the sleeves will be purchased by the Clinical centers. Sleeves should be fitted according to the manufacturer's instructions and used in a disposable manner. Sleeves should be changed when they become soiled or lost their fixation.

IPC should be started just before the surgery in the operating room during general anesthesia induction or after regional anesthesia application before covering the operating field with the sterile material. Also, it is allowed to apply IPC within 12 h after surgery. The main conditions of IPC application are as follows: no venous thrombosis

confirmed by DUS, no skin lesions on the leg, no signs of skin and soft tissue infections of the legs, ABI >0.6.

IPC should be applied around-the-clock in the ICU, and at the time of bed-rest with a 6 h free-of-compression interval from 0 am to 6 am in the profile surgical department. The IPC required to be used during the whole inpatient treatment period.

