#### **5.4. Examination during inpatient treatment**

The following data on surgical procedure should be obtained from the medical records after intervention: the surgical profile (e.g., abdominal, thoracic, neck, pelvis, cranial), type of surgery (open, endoscopic, endoscopy assisted), urgency of surgery (emergent = performed in 0–2 h after admission, urgent = performed in 0–6 days after admission, elective = performed independently at the time of admission), radicalism of surgery (radical, palliative), type of anesthesia (general, regional, combined), surgery duration, blood loss, and intraoperative infusion.

The routine clinical examination of the patient will be performed in a daily manner with special attention to the possible complications, such as DVT, SVT, PE, bleeding, and leg skin injury. IPC sleeves should be removed for 15–20 mins every day for skin inspection and investigation of pedal pulsation. Consultation of any relevant specialist

(cardiologist, neurologist, pulmonologist, infections) should be performed if any complication or development of new co-morbidity will be observed during the follow-up.

DUS should be performed every 3–5 days after surgery and in emergency manner if any clinical suspicion for DVT or SVT appeared. In an emergency manner, DUS may be performed by a blinded expert or specialist on duty on weekend and holidays. However, all conclusions of non-investigational medical staff must be verified by a blinded expert.

SPECT/CT or CTPA should be used to verify PE in an emergency manner if clinical suspicion appeared. An autopsy must be performed in all died patients to verify the absence of DVT and PE.

In case of any clinical suspicion for a VTE event, IPC should be interrupted until final verification of the diagnosis. In the case of positive DUS, CTPA, and SPECT/CT, the therapeutic anticoagulation should be prescribed, and IPC should be removed. In the case of clinical suspicion for VTE with negative results of instrumental tests, IPC should not be returned until the proper diagnosis that mimics VTE will be found.

Any revealed leg skin lesion should be judged individually for the possibility to continue ECS and IPC application. If the decision will be made to stop IPC, the patient should be withdrawn from the study according to the protocol.

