## 6. Patients safety

Administration of the IPC device is a part of standard clinical practice, so patients will be not exposed to additional risk. The most common complication for ECS and IPC is a skin lesion on the legs. However, patients will be monitored for the possibility of developing any of the following: leg skin injury related to mechanical prophylaxis, ischemic changes in the lower limbs, and patient discomfort. There is no reason to expect the incidence would exceed what is encountered in daily practice.

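### Leg skin injury is defined only where stockings touch the skin, and a dedicated daily skin inspection is written only for the IPC arm, so the comparison of this secondary safety endpoint may be distorted

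*Combined protocol and SAP*

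**What the plan says.** The secondary objectives in section 2 include this one: "To study the effect of IPC on the leg skin injury occurrence during inpatient treatment". Section 3.5 lists leg skin injury among the inpatient secondary endpoints. Its definition begins "Leg skin injury is defined as the appearance of skin hyperemia, blisters (and further erosions), and necrosis (and further ulceration", and then limits the site to lesions "in the zone of contact with GCS, especially at the anterior surface of the ankle joint". The Abbreviations list has ECS but not GCS; from the context, GCS almost certainly means the stockings.

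Section 6 has a wider scope. It calls skin lesions the commonest complication of both stockings and IPC, and it monitors "leg skin injury related to mechanical prophylaxis".

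On exposure, section 3 states: "Both groups will receive anti-embolic stockings and injections of LMWH, and patients in the IPC group additionally will receive IPC". Section 4.1 specifies above-knee stockings and says "ECS should be applied round-the-clock during the inpatient period of treatment". Section 4.3 specifies "Kendall SCD™ thigh-length Comfort Sleeves" for the IPC arm.

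On detection, section 5.4 asks for a daily clinical examination without limiting it to one arm, and names leg skin injury among the complications to look for. It then adds: "IPC sleeves should be removed for 15–20 mins every day for skin inspection". It states no matching step for patients who wear stockings alone. Section 3 describes an open-label trial in which blinded assessment is confined to efficacy outcomes.

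**The concern.** Two features of this endpoint do not fit its purpose.

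- **Scope.** The sleeve is the only mechanical device that differs between the arms, and the definition leaves it out. Sections 3.5 and 6 therefore give one outcome two different scopes. A sleeve lesion on skin that no stocking covers would fall outside the literal definition, which would understate harm in the IPC arm.
- **Ascertainment.** A dedicated daily look at the skin is prescribed only where there is a sleeve to remove. The endpoint includes simple hyperemia, a mild sign whose recording is likely to depend on how closely the leg is inspected, and by staff who know the allocation. This could overstate harm in the IPC arm.

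At stake is how one secondary safety comparison can be read. A higher rate with IPC could reflect closer inspection, and similar rates could reflect the two errors offsetting each other.

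**Working it through.** **The plan's own figures.** No rate or power is given for leg skin injury. The only calculation, in section 8, is for the primary endpoint, and it is used here only for the arm size.

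- 30% vs 12%, two-sided 0.05, 80% power: the normal approximation gives 80 per arm, and 90 with continuity correction. Exact Fisher power at 90 per arm is 81.2%. The stated 90 + 90 reproduces.
- 10% withdrawal: 180 / 0.90 = 200. Doubled: 400, taken here as 200 per arm.

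**Scope.** The relevant texts compare as follows.

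| Source | What it covers |
|---|---|
| Section 2, objective | effect of IPC on leg skin injury |
| Section 3.5, definition | stocking contact zone only |
| Section 6, safety | injury from mechanical prophylaxis generally |
| Sections 4.1 and 4.3 | above-knee stockings and thigh-length sleeves, so largely the same skin |
| Section 3.3 | patients with a condition that requires stopping IPC or stockings are withdrawn |

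The last two rows limit the loss. What remains is a sleeve lesion on skin the stocking does not cover, for example after it has slipped. Section 5.6 sets no compliance measure for stockings, so how often this happens would not be known.

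Illustration, with assumed true rates of 5% (control) and 10% (IPC), full detection, and a fraction f of the excess lying outside the stocking zone:

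observed IPC rate = 5% + 5% × (1 − f)

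| f | Observed IPC rate | Observed RR | Fisher power, 200 per arm |
|---|---|---|---|
| 0 | 10% | 2.00 | 41% |
| 0.25 | 8.75% | 1.75 | 25% |
| 0.50 | 7.5% | 1.50 | 13% |
| 0.75 | 6.25% | 1.25 | 5% |

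The overlap of the devices points to the top of this table.

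**Ascertainment.** Let the true rate r be equal in both arms and let s be the proportion of injuries detected.

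observed rate = r × s; observed RR = s(IPC) / s(control)

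Example with r = 10%: 0.10 × 0.90 = 9% and 0.10 × 0.60 = 6%, so RR = 1.5 with no true difference.

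The table gives the probability that a two-sided Fisher test at 0.05 rejects, with 200 per arm and no true difference:

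| Detection, IPC vs control | RR | r = 5% | r = 10% | r = 20% |
|---|---|---|---|---|
| 90% vs 90% | 1.00 | 2.8% | 3.3% | 3.6% |
| 90% vs 80% | 1.125 | 3.1% | 4.4% | 6.3% |
| 90% vs 70% | 1.29 | 4.6% | 8.1% | 15.7% |
| 90% vs 60% | 1.50 | 7.4% | 15.6% | 33.8% |
| 90% vs 50% | 1.80 | 12.0% | 27.9% | 58.7% |

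Every rate and detection proportion in these two illustrations is an assumption. A small gap in detection does almost nothing; a large one would produce false signals of harm.

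**The case against.** The best defence is that the plan already covers most of this.

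- **Overlap.** Everyone is to wear above-knee stockings around the clock, and the sleeves reach the thigh. Shorter stockings are not part of the plan, and a patient who has to stop stockings for a clinical reason is withdrawn under section 3.3. A reader might infer that device harm is being misclassified as a matter of course. The documents do not support that; they support only a small gap at the edges of the zone.
- **Examination of all patients.** The daily examination in section 5.4 applies to both arms and names leg skin injury. Duplex scans of the calf and thigh veins every 3–5 days in both arms presumably expose the legs as well, although they are not skin checks. Nor does section 5.4 say whether stockings come off when sleeves do, so the advantage in seeing stocking-covered skin is unknown. A reader might infer that detection is unequal; the text shows only that it could be.
- **Standing of the endpoint.** It is tempting to call this the main safety outcome for IPC. Section 6 supports its importance, but section 3.5 lists it as one secondary endpoint beside bleeding and others.

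These points stand, and they reduce the concern. They do not remove the mismatch between sections 3.5 and 6, or the fact that a dedicated skin inspection is written for one arm only, with unblinded assessors.

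**Conclusion.** The point holds as a minor matter of definition and ascertainment. As worded, the definition omits the device under test and is narrower than the safety section. The expected loss of sleeve injuries is small because the devices overlap. The extra inspection may raise detection of mild lesions in the IPC arm. Under the assumed detection gaps, equal true harm would appear as a relative risk anywhere from 1.125 (90% vs 80%) to 1.5 (90% vs 60%), and further if the gap were wider.

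Neither effect can be sized from the documents, and because they oppose each other the net direction cannot be stated. A reader might infer that the trial will overstate, or will hide, skin harm from IPC; the text establishes neither. The primary endpoint, its analysis and the sample size do not depend on this.

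**What to change.** - In section 3.5, define the endpoint as injury to skin in contact with stockings or IPC sleeves, replace GCS with a listed abbreviation, and align the wording with section 6.
- Record the site, the lesion type and the device in contact with the skin.
- In section 5.4, state one inspection standard and one skin-status form for both arms, completed at the daily examination already required. Say what is uncovered for that inspection, and reconcile this with the round-the-clock stocking wording in section 4.1; how to reconcile them is for the trial team.

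The cost is a few words in the definition, a short form, and a few more minutes at the daily examination of controls. No design figure changes.

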#### **4. Trial interventions**

All randomized patients will receive a standard VTE prophylaxis according to the Russian National Guidelines, that are complementary to ACCP 9th Edition, contained using of above-knee anti-embolic ECS and LMWH injections. In the experimental group, an IPC device will be applied in adjunction to standard prophylaxis.

##### **4.1. Anti-embolic stockings**

Above-knee anti-embolic compression stockings fitted by the leg size should be applied before the surgery. In the case of elective surgery, the size should be fitted before,

and patients should be admitted to the hospital with their own stockings. In the case of emergent surgery, leg sizes should be obtained after admission, and the stockings should be received from the stocking bank. ECS should be applied round-the-clock during the inpatient period of treatment. After discharge, patients will be recommended to use stocking at night and during the long bed rest for 1 month. The manufacturer for the ECSs is not prespecified, so it is possible to use any available product. Stocking application should be controlled within standard medical care.

#### **4.2. Low-molecular-weight heparins**

Standard doses of 40 mg Enoxaparin (Clexane, Sanofi-Aventis, France) subcutaneously once daily is prespecified. Following Russian National Guidelines, the first injection should be done 12 h before the surgery (elective surgery without high bleeding risk) or within 12 h after surgery (emergent surgery, procedure with high bleeding risk). In the case of the highest bleeding risk, it is allowed to delay the first LMWH injection for 5 days. The patients who did not receive Enoxaparin after 5 days will be withdrawn from the analysis. The pharmacoprophylaxis should be continued until the patient's discharge from the hospital (not less than 7 days) or death. The prolonged prophylaxis with LMWH is not pre-specified and will depend on the surgeon's preference. The enoxaparin administration and the control for injection should be made within the standard clinical practice.

#### **4.3. Sequential pneumatic compression**

Intermitted pneumatic compression should be applied with Cardinal Health™ Kendall SCD™ 700 Series Controller and Kendall SCD™ thigh-length Comfort Sleeves. The pumps will be provided by the Sponsor (10 pumps by Cardinal Health™), and the sleeves will be purchased by the Clinical centers. Sleeves should be fitted according to the manufacturer's instructions and used in a disposable manner. Sleeves should be changed when they become soiled or lost their fixation.

IPC should be started just before the surgery in the operating room during general anesthesia induction or after regional anesthesia application before covering the operating field with the sterile material. Also, it is allowed to apply IPC within 12 h after surgery. The main conditions of IPC application are as follows: no venous thrombosis

confirmed by DUS, no skin lesions on the leg, no signs of skin and soft tissue infections of the legs, ABI >0.6.

IPC should be applied around-the-clock in the ICU, and at the time of bed-rest with a 6 h free-of-compression interval from 0 am to 6 am in the profile surgical department. The IPC required to be used during the whole inpatient treatment period.

## **5. Follow-up**

The follow-up is designed separately for the inpatient and outpatient settings. The total follow-up duration accounts for 6 months.

### **5.1. Baseline examination**

The screening examination is designed to assess patient's eligibility with the inclusion/exclusion criteria. The baseline examination will be performed a day before the surgery in case of elective surgery or just before or within 12 h after the urgent surgery. The basal examination contains the standard diagnostic procedures with special attention to the individual risk factors for postoperative VTE. Patients (or their representatives in case of unconsciousness or deep dementia) should be interviewed for the personal and family VTE history, any obstetrics complications, use of contraceptive pills or other estrogen-containing drugs, and current or previous malignant disorders. Lower limbs should be evaluated for the varicose veins and edema, skin and soft tissue infection, any skin lesions, and pedal pulsation. The relevant co-morbidities, such as congestive heart failure (CHF), chronic obstructive pulmonary disease (COPD), serious lung disease or pneumonia, inflammatory bowel disease, sepsis, lower limb paralysis, and stroke should be evaluated and confirmed according to the medical records and involving other specialists. BMI will be calculated with the data from medical records.

### **5.2. VTE risk assessment**

The primary VTE risk assessment should be performed by Russian National Guidelines, and if the patient will be classified as having a high risk (major surgery in subjects over 60 years old or major surgery in subjects from 40 to 60 years old having additional individual risk factors for VTE), he should be assessed by Caprini score. A Russian adaptation of the 2005 version of the Caprini score will be used (Fig. 3).

The primary risk assessment will be performed before randomization. Any patients that will receive or will be supposed to receive (e.g., supposed prolonged bed rest in ICU, supposed malignancy, CHF, COPD, bowel inflammatory disease, thrombophilia, etc.) a score of 11 or more, should be invited into the study. The calculation of the final Caprini score should be done before discharge or after patients' death. So, all new condition and complications occurred during the inpatient treatment period will be considered. However, some enrolled patients may decrease their score because of unexpected early ambulation, misdiagnosis of malignant disease or other co-morbidities.


Each Risk Factor Represents 1 Point
 
 
 Age 41-60 years
 
 Swollen legs (current)
 
 Varicose veins
 
 Obesity (BMI >25)
 
 Minor surgery planned
 
 Sepsis (<1 month)
 
 Serious Lung disease including pneumonia (<1 month)
 
 Oral contraceptives or hormone replacement therapy
 
 Pregnancy or postpartum (<1 month)
 
 History of unexplained stillborn infant, recurrent spontaneous abortion (<math>\geq 3</math>), premature birth with toxemia or growth-restricted infant
 
 Other risk factors _____
 
 
Subtotal:
	
Each Risk Factor Represents 2 Points
 
 
 Acute myocardial infarction
 
 Congestive heart failure (<1 month)
 
 Medical patient currently at bed rest
 
 History of inflammatory bowel disease
 
 History of prior major surgery (<1 month)
 
 Abnormal pulmonary function (COPD)
 
 Age 61-74 years
 
 Central venous access
 
 Arthroscopic surgery
 
 Malignancy (present or previous)
 
 Laparoscopic surgery (>45 minutes)
 
 Patient confined to bed (>72 hours)
 
 Immobilizing plaster cast (<1 month)
 
 
Subtotal:


Each Risk Factor Represents 5 Points
 
 
 Stroke (<1 month)
 
 Elective major lower extremity arthroplasty
 
 Hip, pelvis or leg fracture (<1 month)
 
 Acute spinal cord injury (paralysis) (<1 month)
 
 Multiple trauma (<1 month)
 
 
Subtotal:
	
Each Risk Factor Represents 3 Points
 
 
 Age 75 years or older
 
 History of DVT/PE
 
 Positive Factor V Leiden
 
 Elevated serum homocysteine
 
 Heparin-induced thrombocytopenia (HIT) (Do not use heparin or any low molecular weight heparin)
 
 Elevated anticardiolipin antibodies
 
 Other congenital or acquired thrombophilia
 
 
If yes: Type _____
 
* most frequently missed risk factor
 
Subtotal:

TOTAL RISK FACTOR SCORE: 
	

**Figure 3.** The 2005 version of the Caprini score, reproduced from Bahl V et al., Ann Surg. 2010;251(2):344-50.

